5.3.2 Pharmacogenomic Studies (Cohort 1 only)

One blood sample per patient will be collected from subjects enrolled in Cohort 1 for pharmacogenetic studies to analyze the genomic DNA and assess genotype of the most relevant drug metabolizing enzymes and transporters (DMET). DNA will be analyzed on a DMET Plus (Affymetrix) genotyping platform that tests for 1,936 genetic variations in 231 drug disposition genes, including 47 CYP (phase I metabolism) genes, 13 non-CYP (phase I metabolism) genes, 78 phase II metabolizing genes (including UGTs), 63 transporters, 4 genes involved in facilitation of drug transporters, 9 genes involved in global regulation of drug metabolizing/transporting proteins, 4 drug binding proteins, and 4 drug targets. The DMET data will be correlated with response and/or toxicity.

5.3.3 Privacy and Confidentiality of medical information/biological specimens

Study procedures and assessments will be done in private clinic rooms. Study related follow up calls will be done from a research office. Subjects will be encouraged to take the call from a private location (such as their home). Slides and tissue blocks will be stored in the Laboratory of Pathology (See section 5.2.2).

Blood samples will be stored in the BPC (See section 5.2.1) .

5.3.4 A Certificate of Confidentiality will be obtained for the study as described in section **12.6.8**.

5.3.5 Management of Results

Subjects will be contacted if a clinically actionable gene variant is discovered. Clinically actionable findings for the purpose of this study are defined as disorders appearing in the American College of Medical Genetics and Genomics recommendations for the return of incidental findings that is current at the time of primary analysis. (A list of current guidelines is maintained on the CCR intranet: <https://ccrod.cancer.gov/confluence/display/CCRCRO/Incidental+Findings+Lists>). Subjects will be contacted at this time with a request to provide a blood sample to be sent to a CLIA certified laboratory.

5.3.4 Genetic counseling

If the research findings are verified in the CLIA certified lab, the subject will be offered the opportunity to come to NIH (at our expense) to have genetic education and counseling with the NCI Genetics Branch to explain this result. If the subject does not want to come to NIH, a referral to a local genetic healthcare provider will be provided (at their expense). This is the only time during the course of the study that incidental findings will be returned. No interrogations regarding clinically actionable findings will be made after the primary analysis.

6 DATA COLLECTION AND EVALUATION

6.1 DATA COLLECTION

The PI or designee will be responsible for overseeing entry of data into an in-house password protected electronic system (C3D) and ensuring data accuracy, consistency and timeliness. The MDASI-BT and/or MDASI-SP survey responses will be entered by study subjects electronically using the CCR Scribe system with data automatically uploaded directly into Labmatrix. The principal investigator, associate investigators/research nurses and/or a contract data manager will assist with the data management efforts. All data obtained during the conduct of the protocol will be kept in secure network drives or in approved alternative sites that comply with NIH security standards. Primary and final analyzed data will have identifiers so that research data can be attributed to an individual human subject participant.

All adverse events, including clinically significant abnormal findings on laboratory evaluations, regardless of severity, will be followed until return to baseline or stabilization of event.

Document AEs from the first study intervention, Study Day 1 through 28 days. Adverse events occurring more than 28 days after the last dose must only be recorded (and reported) if they are considered serious and at least possibly related to research interventions.

An abnormal laboratory value will be recorded in the database as an AE **only** if the laboratory abnormality is characterized by any of the following:

- Results in discontinuation from the study
- Is associated with clinical signs or symptoms
- Requires treatment or any other therapeutic intervention
- Is associated with death or another serious adverse event, including hospitalization.
- Is judged by the Investigator to be of significant clinical impact

If any abnormal laboratory result is considered clinically significant, the investigator will provide details about the action taken with respect to the test drug and about the patient's outcome.

All concomitant medications received within 28 days before the first dose of trial treatment and 28 days after the last dose should be recorded. Concomitant medications administered after 28 days after the last dose should be recorded for serious adverse events (SAEs) and events of clinical interest (ECIs) as defined in sections [8.1.2](#) and [8.1.6](#).

End of study procedures: Data will be stored according to HHS, FDA regulations, and NIH Intramural Records Retention Schedule as applicable.

Loss or destruction of data: Should we become aware that a major breach in our plan to protect subject confidentiality and trial data has occurred, this will be reported expeditiously per requirements in section [7.2.1](#)

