3.6 STUDY CALENDAR

Procedure	Screening	Baseline ¹	Cycles 1-24 (28 \pm 3 days) ¹			28 Days FU ¹¹	Long Term FU ^{10,11}	
			Days ¹				with PD	without PD
			1	8	15			
Marizomib ²			X	X	X			
NIH Advance Directives Form ³		X						
Medical History	X							
Confirmation of Pathology	X							
Height	X							
Physical exam, neurological exam, KPS	X		X			X	X	
Weight	X		X	X ¹²	X ¹²			
Vital signs	X		X ⁴	X ⁴	X ⁴	X	X	
EKG	X	X	X ¹³	X ¹³	X ¹³			
CBC with differential	X		X ⁵	X ⁵	X ⁵	X		
Biochemical profile ⁶	X		X ⁵	X ⁵	X ⁵	X		
Amylase / lipase/CK/ GGT, LDH			X ⁵			X		
Urinalysis	X							
Serum or urine pregnancy test ⁷	X		X ⁵					
PT, INR, aPTT, fibrinogen			X			X		

Procedure	Screening	Baseline ¹	Cycles 1-24 (28+/-3 days) ¹			28 Days FU ¹¹	Long Term FU ^{10,11}	
			Days ¹				with PD	without PD
			1	8	15			
Tumor evaluation (MRI) ⁸	X	X	X			X		X
Concomitant Medications (See 6.1)		X	X	X	X	X		X
Adverse events (See 6.1)		X	X	X	X	X		X
Research blood for SNP Studies		X						
Research blood for Pharmacogenomic Studies (Cohort 1 only)		X						
Collection of archival tumor sample for research studies		X						
MDASI-BT and/or MDASI- S ⁹		X	X			X		X
Phone call or e-mail for survival/new cancer treatments							X	X

¹ Tests done at screening or baseline do not need to be repeated on baseline or Day 1 of Cycle 1 if performed in designated time frame prior to start of study drug. Time window +/- 3 days is allowed for Days 1, 8 and 15.

² 0.8 mg/m² IV.

³ All subjects will complete and sign an NIH advanced directives form which is mandatory on this study.

⁴ See section 3.2 for vital signs schedule on days of drug infusion.

⁵ Labs will be obtained within 72 hours prior to dosing

⁶ Biochemical profile: electrolytes, BUN, creatinine, AST, ALT, total bilirubin, calcium, phosphorus, albumin, magnesium, uric acid

⁷ For women of child-bearing potential only

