8 SPONSOR SAFETY REPORTING

8.1 DEFINITIONS

8.1.1 Adverse Event

Any untoward medical occurrence in a patient or clinical investigation subject administered a pharmaceutical product and which does not necessarily have a causal relationship with this treatment. An adverse event (AE) can therefore be any unfavorable and unintended sign (including an abnormal laboratory finding), symptom, or disease temporally associated with the use of a medicinal (investigational) product, whether or not related to the medicinal (investigational) product (ICH E6 (R2))

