10.4.3 Safety Analyses

Safety will be assessed by reporting the grades of toxicity and the type of toxicity observed for all patients and summarizing data using the descriptive statistics, including mean, standard deviation and confidence intervals.

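### Section 6.1 leaves asymptomatic, untreated Grade 3-4 laboratory values to investigator judgement, and Section 10.4.3 names mean and SD for toxicity but plans no worst-grade incidence

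*Combined protocol and SAP*

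**What the plan says.** **Recording.** Section 6.1 states that "An abnormal laboratory value will be recorded in the database as an AE" only if one of five conditions holds. Three of them are "Is associated with clinical signs or symptoms", "Requires treatment or any other therapeutic intervention" and "Is judged by the Investigator to be of significant clinical impact". The other two are discontinuation from the study, and association with death or another SAE. Follow-up in the same section also turns on clinical significance, not grade: "All adverse events, including clinically significant abnormal findings on laboratory evaluations, regardless of severity, will be followed until return to baseline" or stabilisation.

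**Definition.** Section 8.1.1 is wider. It defines an AE to include "any unfavorable and unintended sign (including an abnormal laboratory finding"), with no further condition. Section 8.1.4 grades each AE by CTCAE version 5.0.

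**Collection.** The Study Calendar (Section 3.6) schedules CBC and the biochemical profile on Days 1, 8 and 15 of each cycle and at the 28-day visit. Its footnote 5 adds "Labs will be obtained within 72 hours prior to dosing".

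**Analysis.** Section 10.4.3, in a sentence that also appears in 10.4.2, first commits to reporting toxicity grades and types for all patients, and then to "summarizing data using the descriptive statistics, including mean, standard deviation and confidence intervals". Safety is a secondary objective (1.1.2) and a secondary endpoint scored by CTCAE version 5.0 (10.1.2). All treated patients are evaluable for toxicity (10.3).

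**The concern.** There are two separate weaknesses.

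The first is in recording. Whether a severe but silent laboratory abnormality becomes an AE depends on one clinician's view of its importance. Because severity is graded per AE, a value that is not entered as an AE gets no grade under the plan. Section 10.4.3 provides no separate laboratory table that would pick it up.

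The second is in reporting. A mean and SD have no clear meaning for an ordinal grade and none for a nominal toxicity type, and those are the only data the sentence names. The plan has no rule for taking each patient's worst grade, no incidence of Grade 3 or higher, and no stated target for the confidence intervals.

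The trial is uncontrolled and plans 50 patients, with 9 or 16 per cohort. A few severe events decide the safety picture, so a reader should be able to count them and two analysts should count them alike.

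**Working it through.** The plan gives no toxicity rate, safety threshold or safety precision figure, so there is none to reproduce. The check sets the texts side by side and then works through the arithmetic of the summary.

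**1. Path of an asymptomatic, untreated Grade 3-4 value through Section 6.1**

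| Condition | Met? |
|---|---|
| Discontinuation from the study | Not usually. Section 3.8 separates leaving the study from stopping therapy, so a value that only stops marizomib does not literally qualify |
| Signs or symptoms | No, by assumption |
| Treatment or other therapeutic intervention | No treatment, by assumption. The plan does not say whether a reduced or skipped dose counts |
| Death or another SAE | Only if linked to one |
| Investigator judges significant clinical impact | Discretionary |

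An example from the plan's own text: Table 4 permits growth factors for Grade 4 neutropenia or neutropenia with fever. Afebrile Grade 3 neutropenia has no treatment listed there, so its recording can rest on the last row alone.

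**2. Sections 6.1 and 8.1.1 and Table 2**

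Under 8.1.1 the same value is an AE. Under 6.1 it may not be. Table 2 then applies grade-based rules to marizomib-related AEs, including a group for other AEs. Under the 8.1.1 definition the value can fall within Table 2. Under the 6.1 rule that depends first on the investigator's view. The three texts need to be reconciled.

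**3. What a mean and SD can show**

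Inputs: n = 9 (Cohort 1 or 2, Section 3.1.1) and one worst grade per patient, with 0 for no toxicity. The profiles are illustrative.

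Mean = sum/9. SD = √[(sum of squares − sum²/9)/8].

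| Profile | Sum | Sum of squares | Mean | SD | Grade 3+ |
|---|---|---|---|---|---|
| 8 × Grade 1, 1 × Grade 4 | 8 + 4 = 12 | 8 + 16 = 24 | 1.33 | √[(24 − 16)/8] = 1.00 | 1/9 |
| 6 × Grade 1, 3 × Grade 2 | 6 + 6 = 12 | 6 + 12 = 18 | 1.33 | √[(18 − 16)/8] = 0.50 | 0/9 |
| 3 × none, 6 × Grade 2 | 12 | 24 | 1.33 | 1.00 | 0/9 |

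The first two profiles share a mean. The first and third share both mean and SD, yet one contains a Grade 4 patient and the other has nobody above Grade 2.

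**4. What an incidence shows**

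For zero events the exact (Clopper-Pearson) two-sided 95% upper limit is 1 − 0.025^(1/n): 33.6% for n = 9, 20.6% for n = 16 and 7.1% for n = 50. For 1/9 the estimate is 11.1%. The lower limit is 1 − 0.975^(1/9) = 0.3%. The upper limit solves (1 − p)^9 + 9p(1 − p)^8 = 0.025, giving 48.2%. The limits follow from cohort size. They are what a reader needs beside a Grade 3+ count, and the plan does not tie its intervals to that count.

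**5. Effect of one missed patient**

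If one patient's only Grade 3-4 event goes unrecorded, the observed rate falls by 1/9 = 11.1 percentage points in Cohort 1 or 2, 1/16 = 6.25 points in Cohort 3 or 4, and 1/50 = 2 points overall (9 + 9 + 16 + 16 = 50, as in Section 10.2).

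**The case against.** **Section 6.1 bars nothing.** A reader might infer that asymptomatic Grade 3-4 values are kept out of the AE data. The documents do not support that. Any one condition is enough, and both the treatment condition and the judgement condition can admit a silent value. The section also asks for the action taken and the outcome of any result considered clinically significant. This stands: capture is discretionary, not blocked.

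**Section 10.4.3 does not say that grades are averaged.** A reader might infer that severe events are diluted away in the report. The sentence begins by committing to grades and types for all patients, so a recorded Grade 4 event would still appear as such. It also plans confidence intervals. This stands too: the weakness is an added summary of an unnamed quantity and the lack of a defined incidence.

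**The number missed may be small.** A reader might apply a general Grade 3-4 laboratory rate to the 50 patients to count those at risk of being missed. The documents give no rate. Such a count would also include events that 6.1 does capture because they are symptomatic, treated, linked to an SAE or judged significant. Section 12.6.1 calls myelosuppression uncommon. Section 1.2.4 reports no Grade 4 related events in the phase I study. The toxicities the protocol stresses are CNS events, which the laboratory rule does not touch. All of this limits the size, but discretionary recording is a weak way to confirm that such toxicity is uncommon.

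**Table 2 is not tied to the database.** Its heading speaks of marizomib-related AEs and says nothing about whether they were entered, so it can be read with the 8.1.1 definition. That is correct. What remains is that the recording rule and the definition differ.

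**The values are not lost.** They are collected at every dosing day, and the team discusses each patient weekly (7.3.1). This stands, and it is why the remedy is cheap.

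**Conclusion.** The point holds as a gap in specification. Section 6.1 has no grade criterion, so capture of asymptomatic, untreated Grade 3-4 laboratory values depends on the investigator, and the rule is narrower than the definition in 8.1.1. Sections 10.4.2 and 10.4.3 name a mean and SD that cannot identify the number of patients with severe toxicity, and they define neither a worst-grade incidence nor a laboratory grade table.

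The size of the recording gap cannot be estimated from the documents. Only its effect per missed patient is known: 11.1 points in a cohort of 9, 6.25 in a cohort of 16 and 2 overall, assuming that the patient has no other Grade 3-4 event in the rate. The reporting illustration assumes one worst grade per patient.

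The analysis concerned is secondary and descriptive, and the PFS6 decision rules are untouched. The change is still worth making: it replaces an undefined summary with a standard one and makes the laboratory toxicity rate reproducible.

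**What to change.** 1. In Section 10.4.3, and in the matching sentence of 10.4.2, replace mean and SD with the number and percentage of patients by worst CTCAE v5.0 grade for each term. Add exact 95% confidence intervals for Grade 3 or higher. Give these by cohort and pooled, on all treated patients.
2. Derive each patient's worst laboratory grade directly from the scheduled CBC and chemistry values, whether or not an AE was entered, and tabulate it.
3. Reconcile the laboratory rule in 6.1 with the AE definition in 8.1.1 and with the grade-based Table 2. State whether a reduced or skipped dose counts as a therapeutic intervention under 6.1.
4. Optionally, add Grade 3 or higher to the list in 6.1. Once laboratory grades are derived, this is no longer essential to the safety rates.

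The cost is a few lines of text, a small amount of programming and, if step 4 is adopted, a little more AE entry. No visit or test is added. The safety table may look less favourable because it will show values that were never entered as AEs.

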6.2 DATA SHARING PLANS

6.2.1 Human Data Sharing Plan

What data will be shared?

I will share human data generated in this research for future research as follows:

- Coded, linked data in an NIH-funded or approved public repository.
- Coded, linked data in BTRIS (automatic for activities in the Clinical Center)
- Coded, linked or identified data with approved outside collaborators under appropriate agreements.

Data will be shared through:

- An NIH-funded or approved public repository: clinicaltrials.gov, dbGaP.
- BTRIS (automatic for activities in the Clinical Center)
- Approved outside collaborators under appropriate individual agreements.
- Publication and/or public presentations.

Data will be shared:

- Before publication.
- At the time of publication or shortly thereafter.

6.2.2 Genomic Data Sharing Plan

Unlinked genomic data will be deposited in public genomic databases such as dbGaP in compliance with the NIH Genomic Data Sharing Policy.

6.3 RESPONSE CRITERIA

The primary endpoint is progression-free survival at 6 months (PFS6). A combination of the neurological examination and MRI will be used to define progression. Due to improvements in neuroimaging and the

fact that tumor growth in certain regions of the CNS is without immediate neurologic signs and symptoms, greater reliance is placed on neuroimaging to define progression.

6.3.1 Disease Parameters

Measurable Disease: Bi-dimensionally measurable lesions with clearly defined margins by MRI. All tumor measurements must be recorded in millimeters (or decimal fractions of centimeters). Based on RANO criteria **Table 6** [26].

Objective Status: To be recorded at each evaluation: If there are too many measurable lesions to measure at each evaluation, choose the largest two to be followed before a patient is entered on study. The remaining lesions will be considered evaluable for the purpose of objective status determination. Unless progression is observed, objective status can only be determined when ALL measurable and evaluable sites and lesions are assessed.

Time to Treatment Failure: From date of registration to the date of first observation of progressive disease, non-reversible neurologic progression or permanently increased steroid requirement (applies to stable disease only), death due to any cause, or early discontinuation of treatment.

6.3.2 Methods for Evaluation of Measurable Disease

All measurements should be taken and recorded in metric notation using an electronic measurement tool available through the imaging software. All baseline evaluations should be performed as closely as possible to the beginning of the treatment and never more than 2 weeks before the beginning of the treatment.

The same method of assessment and the same technique should be used to characterize each identified and reported lesion at baseline and during follow up. Imaging-based evaluation is preferred to evaluation by clinical examination unless the lesion(s) being followed cannot be imaged but are assessable by clinical exam.

6.3.3 RANO Disease Response Criteria

For the purposes of this study, patients should be re-evaluated for response every 8 weeks. Confirmatory scans should also be obtained in 4-8 weeks period of time following initial documentation of objective response.

Table 6: RANO Criteria for Response

RANO Criteria for Response (28)	CR	PR	SD	PD
T1 gadolinium enhancing disease	None	≥ 50% ↓	< 50% ↓ but < 25% ↑	≥ 25% ↑ ¹
T2/FLAIR	Stable or ↓	Stable or ↓	Stable or ↓	↑ ¹
New lesion	None	None	None	Present ¹
Corticosteroids	None	Stable or ↓	Stable or ↓	n/a [†]
Clinical status	Stable or ↑	Stable or ↑	Stable or ↑	↓ ¹
Requirement for response	All	All	All	Any ¹

RANO Criteria for Response (28)				
	CR	PR	SD	PD

¹ Progression occurs when this criterion is present
 
† Increase in corticosteroids alone will not be taken into account in determining progression in the absence of persistent clinical deterioration.
 
↓ = decreased, ↑ = increased,
 
CR = complete response, PR = partial response, SD = stable disease, PD = progressive disease. If PD is unclear based on white matter changes, patients may be kept on trial.
 
FLAIR, fluid-attenuated inversion recovery; NA, not applicable.
				

Stable/No Progression (SD): No evidence of new measurable lesions on MR imaging. The designation of Stable/No Progression requires a minimum of 12 weeks duration. All measurable and evaluable sites must be assessed using the same techniques as baseline.

Partial response (PR): ≥ 50% reduction in the sum of products of all measurable lesions over baseline sum observed using the same techniques as baseline. The patient must be on a stable or decreased dose of corticosteroids to be evaluable for response.

Complete response (CR): Complete resolution of all lesions. The patient cannot be on any corticosteroids with the exception of adrenal replacement doses.

Progression (PD): 25% increase in the sum of products of all measurable lesions over smallest sum observed (over baseline if no decrease) using the same techniques as baseline, OR clear worsening of any evaluable disease, OR appearance of any new lesion/site, OR failure to return for evaluation due to death or deteriorating condition (unless clearly unrelated to this cancer).

Unknown: Progression has not been documented and one or more measurable or evaluable sites have not been assessed.

NOTE: Steroids: Steroid dosage will be carefully monitored and recorded during each course of therapy and steroid dosage changes will be considered before response determinations are made.

6.3.4 Evaluation of Best Overall Response

The best overall response is the best response recorded from the start of treatment until disease progression/recurrence (taking as reference for progressive disease the smallest measurements recorded since the treatment started). The patient’s best response assignment will depend on the achievement of both measurement and confirmation criteria.

6.3.5 Duration of Response

Duration of overall response: The duration of overall response is measured from the time measurement criteria are met for CR or PR (whichever is first recorded) until the first date that recurrent or progressive disease is objectively documented (taking as reference for progressive disease the smallest measurements recorded since the treatment started).

The duration of overall CR is measured from the time measurement criteria are first met for CR until the first date that progressive disease is objectively documented.

Duration of stable disease: Stable disease is measured from the start of the treatment until the criteria for progression are met, taking as reference the smallest measurement recorded since the treatment started, including the baseline measurements.

